## **9.6. Other Safety Data**

### **9.6.1. Liver Function Tests (LFTs)**

LFT data will be collected at each visit and summarized descriptively by laboratory (central, local), study part, dose cohort, and overall. The following laboratory tests will be collected: albumin, alkaline phosphatase, direct bilirubin, indirect bilirubin, total bilirubin, ALT, and AST. LFT data will also be presented in a listing. In addition, ALT, and AST levels and Total bilirubin will be plotted by-participant and laboratory (central, local) over time.

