- B If a site is not able to administer FLT201 the Sponsor will attempt to identify an alternative site for the infusion week only.
- C Height (screening only) and weight will also be measured.
- D Vital signs include pulse, blood pressure, respiratory rate, and temperature.
- E Participants will complete BPI-SF questionnaire once a day covering the 7 days following each screening visit, and then for 7 consecutive days, on each occasion commencing at the start of Weeks 4, 12, 24 and 37 post-treatment (week prior to the 38-week visit). Study sites will contact participants at the beginning of Week 37 to remind them to complete the questionnaires during Week 38.
- F Participants will complete the FACIT-Fatigue questionnaires at the end of each week during the screening period, and then at the end of Weeks 4, 12, 24, and 37 post treatment.
- G A weight-based tapering immunosuppressive regimen will be initiated at the Week 3 visit. Cohort 1 may not require immunosuppression. For details see the pharmacy manual.
- H Serum pregnancy test performed only at Week 1 to EOS and unscheduled visits if the urine pregnancy test is positive.
- I Testing to be performed twice weekly (including the testing as part of the scheduled study visit), initially commencing at Week 1 and concluding at the end of Week 9 and later commencing at Week 28 and concluding at the end of Week 38/EOS. The tests should be as evenly spaced through the week as possible, for example: Monday and Thursday, or Tuesday and Friday.
- J Testing to be performed three times weekly (including the testing as part of the scheduled study visit), commencing at Week 10 and concluding at the end of Week 27. The tests should be as evenly spaced through the week as possible, for example Monday, Wednesday, and Friday.
- K Local testing. Weekly CMV PCR testing for the duration the participant is taking tacrolimus in the immunosuppressant regimen. Tests should be undertaken to coincide with use of tacrolimus if outside of the prophylactic regimen. CMV IgG testing followed by CMV PCR. CMV PCR only indicated for a positive CMV IgG.
- L Local testing. Tacrolimus levels should be tested twice weekly until levels are in the therapeutic range and weekly thereafter for the duration the participant is taking tacrolimus in the immunosuppressant regimen. Tests should be undertaken to coincide with use of tacrolimus if outside of the prophylactic regimen.

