8.1 Study Description

This is a first in human, Phase 1/2, open label, safety, tolerability, and efficacy study in adult patients with Gaucher disease type 1.

Participants will undergo the screening assessments described in Section 12.1.1 and Section 12.1.2. for up to 16 weeks prior to Study Day 1 (gene therapy infusion).

In Part 1, eligible participants currently receiving ERT/SRT will maintain their current treatment until a minimum of 2 consecutive results at least 4 weeks post-dosing show leukocyte GCase activity level higher than pre-dose trough GCase activity level, after which ERT/SRT may be withdrawn.

Progression from Part 1 to Part 2 will be by a substantial protocol amendment, based on safety/tolerability (including DLT), PK, PD, and clinical data.

In Part 2, eligible participants will be PUPs. Participants may need to be considered for initiation of ERT/SRT in case of a lack of a trend to normalisation in leukocyte GCase activity level in serial measurements from at least 4 weeks post-dosing, suggestive of low probability of clinical efficacy.

Treatment-eligible participants will report to the infusion study site on the day prior to receiving the gene therapy infusion (Day -1). Participants will either attend their local study site if it has been approved for FLT201 infusion, or if not, an alternative approved infusion study site. On Day 1, FLT201 will be administered as a single-dose, slow IV infusion into a peripheral vein, and the participant will remain in the study centre for at least 8 hours until the investigator has deemed the participant as fit to be discharged.

Participants will be required to undergo study evaluations at intervals over the 9-month post -treatment period. These will take place either at the study infusion site or at their local study site.

The study will be conducted in 2 parts (Figure 3):

[figure not shown]

Figure 3: Study Schema

Part 1: Dose Escalation in Previously Treated Patients

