## **4. General Statistical Considerations**

All study data collected will be presented in data listings, and all relevant data will be tabulated and summarized by study part, dose cohort, and overall, unless stated otherwise.

Continuous data will be described using descriptive statistics (i.e., n, mean, standard deviation, median, minimum, and maximum). Categorical data will be described using the count and percentage in each category. For the summary statistics of all numerical variables unless otherwise specified, minimum and maximum will be displayed to the same level of precision as reported. Mean and median will be displayed to one level of precision greater than the data collected. Standard deviation, standard error, and confidence intervals will be displayed to two levels of precision greater than the data collected.

Missing data will not be imputed. All analyses will be based on observed cases for the safety population unless specified otherwise.

Clinical laboratory and PK results that are below the lower limit of quantification (BLQ/LOQ), below the limit of detection (LOD), above the upper limit of quantification (ULOQ) or missing will be displayed as such in the data listings.

To calculate descriptive statistics and PK parameters, all BLQ, LOQ and LOD results will be treated as half of the BLQ/LOQ/LOD values whereas all ULOQ values will be treated as the ULOQ values as applicable.

The end of the study will be defined as the last visit by the last participant. All participants will be followed up for at least 5 years in a separate long-term follow-up study.

Unless specified otherwise, baseline will be defined as the last non-missing measurement prior to the infusion of IMP.

Change from baseline is defined as: post-baseline value – baseline value.

Study Day 1 is the calendar day of the IMP infusion. Subsequent study days are calculated as the date of assessment/event – date of infusion + 1. Pre-infusion study days are calculated as date of assessment/event – date of infusion. There is no Study Day 0.

All data are summarized based on the visit name collected on the eCRF page.

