## 6. Demography and Baseline Characteristics

### 6.1. Demography

Demography data will be summarized by study part, dose cohort, and overall. Individual participant listings will be provided to support the summary table.

Age (year), weight (kg), height (cm) and body mass index (BMI) will be summarized using descriptive statistics (i.e., n, mean, standard deviation, median, minimum, and maximum). Age

category (year), race, sex, ethnicity, and other categorical variables (see list below) will be summarized with frequency tabulations.

Other characteristics include:

- Age group (<65 years, ≥65 years);
- Region (Europe, North America, Latin America);
- Screening hemoglobin level;
- Screening platelet count;
- Screening GCase activity levels (Plasma and DBS);
- Screening GCase concentration;
- Screening chitotriosidase activity (DBS);
- Screening Lyso-Gb1 (Plasma and DBS);
- Screening liver volume (multiples of normal);
- Screening spleen volume (multiples of normal);
- Screening bone mineral density T-score (Lumbar spine and Hips);
- Screening bone mineral density Z -score (Lumbar spine and Hips);
- Screening pulse rate (beats per minute);
- Screening blood pressure (mmHg);
- Screening respiratory rate (breaths per minute);
- Screening body temperature (°C);

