### **9.2. Clinical Laboratory Evaluations**

Summary tables presenting observed values and changes from baseline will be presented for clinical laboratory tests with numeric values by study part, dose cohort, and overall, for participants in the Safety Set. Changes from baseline to each scheduled post-baseline visit will be presented.

Laboratory assessments will be performed by a central laboratory. All summaries will be based on the units provided by the laboratory; no conversion will be applied.

All relevant clinical laboratory test results will be classified as Low, Normal, and High, or Normal/Abnormal according to the normal ranges. These categorical data will be summarized in shift tables comparing the results at each scheduled post-baseline visit with those at the baseline visit.

When there are multiple values within a visit for a particular laboratory variable, the worst value will be taken (worst being the smallest value for criteria below a certain threshold or the largest value for criteria above a certain threshold). If a participant has a value below the threshold and above the threshold, the value furthest from the threshold will be chosen.

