### **9.2.1. Hematology**

All hematology central laboratory tests will be summarized: complete blood count with differential, platelet count, prothrombin time (PT), international normalized ratio (INR), and activated partial thromboplastin time (APTT). All hematology data by participant will be presented in a listing. Note that in the occasions where central laboratory results are missing, local laboratory results will be summarized and listed.

Additionally, plots by-participant for hematology central laboratory tests over time will be produced for the following tests: hemoglobin, platelet count, APTT, and PT.

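### Local liver tests from several sites' laboratories are pooled on the raw scale, with no rule putting them in a common unit

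*SAP*

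**What the plan says.** SAP 9.6.1 gives the summary rule for liver function tests: "LFT data will be collected at each visit and summarized descriptively by laboratory (central, local), study part, dose cohort, and overall". The split is by type of laboratory only, so every site's local laboratory falls into one local stratum. No unit and no scaling to the upper limit of normal (ULN) is specified. ALT, AST and total bilirubin are also plotted by participant and laboratory type, and all values are listed.

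The only unit rule for laboratory results is in SAP 9.2: "All summaries will be based on the units provided by the laboratory; no conversion will be applied". The sentence before it says that laboratory assessments are done centrally. The same section plans that "Summary tables presenting observed values and changes from baseline will be presented for clinical laboratory tests with numeric values", and adds shift tables (low, normal, high) against normal ranges. SAP 9.2.1, under that heading, brings in local values: "Note that in the occasions where central laboratory results are missing, local laboratory results will be summarized and listed".

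Under SAP 4, "baseline will be defined as the last non-missing measurement prior to the infusion of IMP". SAP 6.1 lists "Region (Europe, North America, Latin America") as a demographic category. Protocol 8.1 has participants attend their local site for infusion "if it has been approved for FLT201 infusion, or if not, an alternative approved infusion study site", and Protocol 10.2.2 says that where a site cannot infuse, "the Sponsor will attempt to identify an alternative site for the infusion week only".

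**The concern.** A mean, SD or maximum over values in different units has no meaning. With about three participants per cohort (about 12 across about 4 cohorts in Part 1), one value in another unit can decide what the table shows. Bilirubin and albumin are the LFT analytes most exposed, because each is commonly reported in more than one unit.

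Change from baseline has a further weakness. Protocol Table 1 schedules no local LFT at screening. The scheduled local LFTs before infusion are those on Day -1 and on Day 1 pre-dose (Protocol Table 2), both at the infusion site. A participant infused elsewhere and followed at home would have a baseline from one laboratory and follow-up from another.

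The protocol itself allows for such differences. Its ALT adverse-event-of-special-interest rule (Protocol 14.2.9) requires the consecutive rise to be seen within one laboratory, and its liver exclusion criterion (Protocol 9.2) is set in multiples of the ULN. The SAP tables carry neither safeguard into the summaries of a first-in-human study whose primary objective is safety and whose anticipated class effect is on the liver.

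**Working it through.** The documents state no figure on this point, so there is none to reproduce. The check is a reading of the rules, a sample count and a worked example.

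**Which rule covers local LFTs.** SAP 9.6.1 is silent on units. The SAP 9.2 rule says all summaries but follows a sentence about the central laboratory. If it reaches local LFTs, it rules out conversion. If it does not, no unit rule exists for them. Either way, nothing requires a common unit.

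**Sample count (Global schedule, Weeks 1-38; Protocol Table 1 and 12.2.1).**
- Local: twice weekly in Weeks 1-9, three times weekly in Weeks 10-27, twice weekly in Weeks 28-38: 9 x 2 + 18 x 3 + 11 x 2 = 18 + 54 + 22 = 94.
- Central: Weeks 1-12 plus 14, 16, 20, 24, 28, 32 and 38: 12 + 7 = 19.
- Local share of planned samples: 94 / (94 + 19) = 83%.
- Local draws beyond one per scheduled visit: 94 - 19 = 75.

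**Conversion factors (assumed; not in the documents).** Bilirubin molar mass 584.66 g/mol, so 1 mg/dL = 10 mg/L, and 10,000 / 584.66 = 17.1 umol/L. For albumin or haemoglobin, 1 g/dL = 10 g/L.

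**Hypothetical cohort of three, total bilirubin.** Participant A's laboratory reports mg/dL (0.6 rising to 2.5). B and C are in umol/L (8 to 9, and 10 to 11). Converted, A goes from 10.3 to 42.8, a change of +32.5.

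| Statistic | Raw values pooled | All in umol/L |
|---|---|---|
| Post-dose mean | (2.5 + 9 + 11)/3 = 7.5 | (42.8 + 9 + 11)/3 = 20.9 |
| Post-dose maximum | 11 | 42.8 |
| Mean change | (1.9 + 1 + 1)/3 = +1.3 | (32.5 + 1 + 1)/3 = +11.5 |

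The raw table gives C's value as the maximum and hides A's rise.

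**Laboratory change after the infusion week (hypothetical).**
- No true change, baseline 0.6 mg/dL, follow-up in umol/L: 10.3 - 0.6 = +9.7 at every visit.
- True doubling, baseline 10.3 umol/L, follow-up 20.5 umol/L reported as 1.2 mg/dL: 1.2 - 10.3 = -9.1, that is -9.1/10.3 = -88%. A doubling appears as a fall.

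**Same unit, different reference range (ULNs assumed).** ALT of 50 U/L is 50/35 = 1.43 x ULN in one laboratory and 50/55 = 0.91 x ULN in another.

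**Range.** With one unit throughout, the unit error is zero and only the last effect remains. With mixed units, an individual value can be off by a factor of 17.1 for bilirubin or 10 for albumin.

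**The case against.** The strongest reply is that the no-conversion sentence belongs to the central laboratory, where one set of units makes it sensible. A reader might infer that the SAP forbids converting local LFTs; its text does not say so. That stands, and the point is therefore put as a missing rule beside a general sentence that points the wrong way.

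The shift tables are a real partial safeguard if SAP 9.2 governs local LFTs. Classification against each laboratory's own range needs no conversion, so a raised bilirubin would still be classed as high. They do not show the size of a rise, and they do not correct the means, maxima or changes. If SAP 9.2 does not govern local LFTs, neither these tables nor its change-from-baseline tables are promised for them. SAP 9.6.1 itself mentions only descriptive summaries, although SAP Table 2-1 and Protocol 15.3 call for change from baseline in laboratory data generally.

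Three stronger readings are tempting but unsupported:
- That 83% of the LFT table content is at risk. The figure is a share of planned samples. SAP 4 summarises by eCRF visit name, the SAP does not say that the 75 between-visit draws enter those tables, and each of the 19 scheduled visits also has a separately summarised central LFT.
- That DLT decisions are compromised, because bilirubin determines whether a severe transaminase rise counts as a DLT under the Global definition. DLTs and events of special interest are judged on individual participants, not from these pooled tables.
- That the haemoglobin endpoint is compromised. No local haematology is scheduled, so an error would need a missing central value, an ad hoc local one and mismatched units together.

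Units may also be harmonised under the data management plan (Protocol 16.1.4), which is not available here. An odd value would probably be noticed in the listings or by-participant plots. But the plots share the problem: a change of laboratory can produce a false jump there too.

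**Conclusion.** The point holds as a conditional weakness in the analysis plan. Local LFTs from several laboratories are summarised as one raw-scale stratum, no rule puts them in a common unit, and the only unit rule that exists is not confined to central data. If local laboratories report different units and nothing upstream standardises them, pooled local bilirubin and albumin summaries will be wrong, and so will any local change from baseline for participants whose infusion-week laboratory uses another unit. The conclusion rests on facts the documents do not give: site units, and how many participants are infused away from home.

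For ALT and AST no difference in units has been shown; the exposure there is reference range only. Central LFT tables, listings, counts of TEAEs, events of special interest and DLTs, and dose decisions are unaffected. This is a minor correction, worth making because it is cheap and concerns a main safety display.

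**What to change.** Amend the SAP only; no protocol amendment is needed.

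- In SAP 9.2, keep the no-conversion sentence but restrict it to central-laboratory data, and add: *Local laboratory results will be converted to the central laboratory's unit for each analyte before any summary or plot, including local haematology used under 9.2.1.*
- In SAP 9.6.1, also present local ALT, AST and total bilirubin as multiples of the reporting laboratory's ULN. Compute any local change from baseline on that scale, or only where baseline and follow-up come from the same laboratory.

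The cost is a few sentences and a little extra programming. Local units and reference ranges must be in the database. Neither document confirms that they are, although judging a local ALT to be above normal for the special-interest rule already requires the range at site level.

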### **9.6.2. Tacrolimus Levels and CMV Testing**

A listing displaying cytomegalovirus (CMV) testing results throughout the study will be presented. In addition, a line plot by participant displaying tacrolimus levels over time will be presented for all participants who received at least one dose of tacrolimus.

### **9.6.3. Serology Screening**

The following serology tests will be listed: HBsAg, HepCAb, anti-HIV1/2 antibodies, CMV IgG antibodies, CMV PCR and SARS-CoV-2 (COVID-19).

## **10. Pharmacokinetics**

All PK listings and individual concentration-time profiles will be presented using the safety Set. PK tables, mean figures and all statistical analyses will be presented using the PK Set.

### **10.1. Data Handling**

Data rounding specifications for PK data are documented in the PK tables, listings, and figures shells.

Plasma, leukocyte, and dried blood spot (DBS) glucocerebrosidase (GCase) activity levels that are BLQ or missing will be displayed as such in the data listings.

For the calculating of descriptive statistics and PK parameters, all BLQ values will be treated as half of the lower limit of quantification.

GCase activity levels will be baseline adjusted. Baseline is defined as any collection before the administration of the IMP. An average of the screening and pre-dose collection results will be taken to determine baseline for each of the matrices. Baseline adjustment leading to results <0 will be reported as 0.

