12.1.4 Infusion (Day 1)

The following assessments will be conducted:

- Vital signs (pulse, blood pressure, respiration rate, and temperature) will be monitored -1 hours before the infusion and at 15-minute intervals (± 5 mins) from the start to completion of infusion. Vital signs will continue to be monitored hourly from the end of infusion (± 10 mins) i.e., +1, +2, 3, 4, 5, and 6 hours. Following 8-hour post-dosing monitoring, additional 2-hourly monitoring can occur, if deemed necessary by the investigator.
- IV catheter insertion into a suitable peripheral vein (e.g., the median cubital vein).
- The IV catheter will be flushed with saline.
- The vector will be thawed and prepared in accordance with the instructions in the FLT201-01 Pharmacy Manual
- Prepared drug will be kept at room temperature prior to administration.
- At approximately 1 hour prior to vector infusion, the investigator or designee will assess the participant's vital signs and blood samples will be collected to analyse:
 - LFTs (local laboratory analysis).
 - GCase activity level (central laboratory analysis).
- The prepared drug containing the calculated vector dose will be infused through the catheter using an appropriate syringe driver, according to the FLT201-01 Pharmacy Manual
- On completion of the infusion, the catheter will again be flushed with saline.
- AEs and concomitant medications will be captured throughout the day.
- LFTs (local laboratory analysis): will be repeated 6 hours after infusion.
- Participants will remain at the infusion centre for at least 8 hours post-infusion to observe any immediate toxicity of the procedure. If the vital signs are stable, the catheter will be removed prior to participant discharge from the centre.
- Participants may be discharged from the study site. All participants will receive a medical alert card.

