### **10.3. Plasma, Leukocyte and DBS Pharmacokinetic Parameters**

Plasma, leukocyte, and DBS GCase baseline adjusted activity level-time data will be analyzed by non-compartmental analysis using Phoenix® WinNonlin® Version 8.3 or higher (Certara USA, Inc., Princeton, NJ). The following PK parameters will be calculated for baseline adjusted GCase activity levels, where data permit:

$C_{\max}$	Maximum observed concentration.
$T_{\max}$	Time of maximum observed concentration.
$AUC_{\text{last}}$	AUC from time 0 to the last measurable observed concentration ( $C_{\text{last}}$ ), calculated using the linear trapezoidal rule.

Actual sampling times will be used for the estimation of all PK parameters, and all available GCaSe activity level data will be included in the analysis (including resulting from samples collected outside predefined collection windows).

Plasma, leukocyte, and DBS PK parameters will be presented in data listings and summarized separately using descriptive statistics (number of observations, arithmetic mean, SD, CV, geometric mean, geometric CV, median, minimum, and maximum) by study part and cohort.  $T_{\max}$  will be summarized using number of observations, median, minimum, and maximum only.

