#### 10.4. Pharmacokinetic Statistical Analyses – Dose Proportionality (Power Model)

A non-linear Power Model will be used to assess dose-proportionality for baseline adjusted GCaSe Activity Levels in Part 1 of the study in all matrices (plasma, leukocytes, DBS). Actual dose received by each patient will be used. The proportional relationship between the expected value of each parameter  $E(y)$  and dose is written as a power function:

$$E(y) = \alpha * \text{dose}^{\beta} \text{ [Equation 1]}$$

where ' $\alpha$ ' is a constant, ' $\beta$ ' is the proportionality constant and ' $y$ ' is the parameter of interest. The exponent,  $\beta$ , will be estimated by performing a linear regression of  $\ln(\text{parameter})$  [ $C_{\max}$  and  $AUC_{\text{last}}$ ] versus  $\ln(\text{dose})$ . The exponent,  $\beta$ , is the estimated slope of the resulting regression line, since taking logs of Equation 1 gives the linear relationship:

$$\ln(y) = \alpha + \beta * \ln(\text{dose}) \text{ [Equation 2]}$$

The relationship is dose proportional when  $\beta = 1$ .

Linear regression plots of systemic exposure ( $C_{\max}$  and  $AUC_{\text{last}}$ ) versus dose will be presented using log-log scales with the power model overlaid.

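### SAP 10.1 sets negative baseline-adjusted GCase to zero without saying whether this covers the secondary change-from-baseline summary, its baseline is not tied to ERT timing, and no rule covers a zero Cmax or AUClast

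*SAP*

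**What the plan says.** SAP 10.1 (Data Handling) baseline-adjusts GCase activity. On the baseline it says "An average of the screening and pre-dose collection results will be taken to determine baseline for each of the matrices", and on the result, "Baseline adjustment leading to results <0 will be reported as 0". Neither sentence is limited to a particular output.

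SAP 4 gives the general rule: "Unless specified otherwise, baseline will be defined as the last non-missing measurement prior to the infusion of IMP". It defines change from baseline as the post-baseline value minus the baseline value, with no floor. SAP 10.2 then plans summaries of observed values and changes from baseline, and plots of raw values by participant. It does not say whether its changes use the 10.1 adjustment.

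SAP 10.3 derives Cmax and AUClast from the adjusted data, using all available samples, and summarises them with statistics that include "geometric mean, geometric CV, median, minimum, and maximum". In SAP 10.4 the dose-proportionality exponent "will be estimated by performing a linear regression of" the log parameter on log dose, for Part 1 and for plasma, leukocytes and DBS. There is no rule for a parameter equal to zero.

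On background therapy in Part 1, Protocol 8.1 says that "eligible participants currently receiving ERT/SRT will maintain their current treatment" until at least two consecutive results, 4 weeks or more after dosing, "show leukocyte GCase activity level higher than pre-dose trough GCase activity level". The Day 1 GCase sample is timed to FLT201: "At approximately 1 hour prior to vector infusion" (Protocol 12.1.4). No supplied section times a GCase sample to the ERT infusion.

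**The concern.** The secondary PK endpoint is change from baseline in plasma and leukocyte GCase activity. A floored change cannot be negative, so noise around no change becomes a positive mean, and a fall disappears from the change table. Two programmers could reasonably produce different tables from SAP 4 and SAP 10.1.

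The baseline raises a second question. For ERT-treated participants it may contain infused enzyme, in an amount that depends on when the sample was taken. After withdrawal that share is still subtracted although it is no longer present, which biases the change downward. While ERT continues, infused enzyme in a post-dose sample can be counted as FLT201 exposure. Since Cmax is a maximum, one sample near an ERT peak can set it.

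Third, a participant whose adjusted profile is zero throughout still belongs to the PK Set, because one measurable result is enough (SAP 4.4.3). That participant has no log and so cannot enter the regression or the geometric mean. Such a loss would fall on the least responsive participants.

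**Working it through.** The documents give no figure on this point to reproduce. The within-person SD of GCase activity, written s, is not stated, so results are in units of s.

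**1. Floor at one visit.** There are two scheduled pre-dose GCase activity samples, Screen 1 (Protocol Table 1) and Day 1 pre-dose (Table 2). Baseline is their mean, with variance s²/2. The change therefore has variance s² + s²/2 = 1.5s², that is, SD τ = 1.225s. For a true change μ, with Φ and φ the standard normal distribution and density functions:

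E[max(X, 0)] = μ·Φ(μ/τ) + τ·φ(μ/τ)

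| True change (s) | Mean after floor (s) | Bias (s) |
|---|---|---|
| −1.75 | +0.04 | +1.79 |
| 0 | +0.49 | +0.49 |
| 1 | 1.14 | +0.14 |
| 2 | 2.03 | +0.03 |
| 3 | 3.003 | +0.003 |

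Check at zero: 1.225 × 0.399 = 0.49. The floor matters only when the true change is small or negative.

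**2. When ln(0) arises.** A zero at one visit does no harm to the regression. Cmax is zero only if all 20 scheduled post-dose samples (Day 3; Weeks 1–12, 14, 16, 20, 24, 28, 32, 38) lie at or below baseline. For a participant with no expression, with baseline raised by k·s above every post-dose level:

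P(Cmax = 0) = ∫ f(b)·Φ(b + k)²⁰ db, where f is the normal density with mean 0 and variance 0.5.

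This gives 1.5%, 16%, 57% and 90% for k = 0, 1, 2 and 3. For k above 0 these are upper figures. Protocol 8.1 keeps ERT/SRT going for at least 4 weeks and makes withdrawal depend on achieved GCase activity, so early samples are also on therapy. If the first five (Day 3, Weeks 1–4) carry the same ERT contribution as baseline, the integrand becomes f(b)·Φ(b)⁵·Φ(b + k)¹⁵, and the results for k = 1, 2 and 3 are 7%, 11% and 11%.

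**3. Slope of the power model.** The simulation used 12 participants, three per planned dose, and a true slope of 1, and dropped zeros. Assumptions not in the documents: s = 0.3 × baseline, between-person CV 50%, and baseline inflation that is absent after dosing. Results for AUClast:

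| Rise at lowest dose (× baseline) | Baseline inflation (× baseline) | Slope, floored | Slope, unfloored | Trials with any zero |
|---|---|---|---|---|
| 1 | 0 | 1.01 | 1.01 | 0% |
| 1 | 1 | 1.65 | 1.32 | 38% |
| 0.5 | 1 | 1.90 | 1.41 | 89% |
| 50 | 0 to 2 | 1.00–1.02 | 1.00–1.02 | 0% |

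With a clean baseline and a rise of 1× baseline, the floor leaves the slope alone. The distortion comes mainly from the assumed inflation, and the floor adds to it.

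**4. The protocol's own expectation.** Protocol 6.5.2 scales linearly from non-human primates: 336 × (4.5×10¹¹ / 2×10¹²) = 75.6 and 1308 × 0.225 = 294.3 nmol/h/mL, in line with its 76 to 295. The example lower limit of normal in Protocol 13.3.1.2, 1.5 µmol/L/h, equals 1.5 nmol/h/mL, although its matrix is not stated. The ratios are 75.6/1.5 = 50 and 294.3/1.5 = 196. If plasma expression is of that order, neither the floor nor the baseline has a visible effect on the plasma slope. No projection is given for leukocytes or DBS, and 13.3.1.2 plans for a first participant below the normal range.

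**The case against.** The strongest reply is that "baseline adjusted" is the term used for the non-compartmental analysis and the power model, so the floor may never have been meant for the 10.2 changes, and SAP 4 then governs. That is a possible reading, but 10.1 states the rule without limit, so the text does not settle it.

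A reader might infer that the floor conceals loss of expression. It does not: SAP 10.2 also plans observed summaries, individual listings and raw plots, and the arithmetic mean, median and minimum of Cmax and AUClast keep zeros.

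A reader might also infer that the log-log model is broken. The documents do not support that. A missing log needs a whole post-dose profile at or below baseline, and under the protocol's plasma projection this does not occur in the simulation. The steep slopes above rest on an ERT offset that no document quantifies.

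The size of any ERT contribution is open. Protocol 6.5.3.3 describes peaks in plasma as brief, and the laboratory manual, not supplied, may set sampling times. SRT users and treatment-naive Part 2 participants receive no infused enzyme at baseline. Finally, the study is descriptive, dose response is exploratory, and the GCase escalation rule compares activity with the normal range rather than with floored values. All of this stands and limits the severity, but it does not remove the need for a clear rule.

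**Conclusion.** The point holds at moderate severity, in three parts of unequal certainty.

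- **Floor.** The text of 10.1 conflicts with the signed change in SAP 4. If the floor is applied in 10.2, the bias is +0.49 s at no change and negligible from about 2 s upward, and falls below baseline are reported as roughly zero. This rests on normal errors and a two-sample baseline.
- **Baseline.** It is not linked to ERT timing in the supplied documents, the trough in Protocol 8.1 is undefined and not carried into the SAP, and 10.3 pools on-ERT with off-ERT samples. The effect is of unknown size and pulls the change in the opposite direction to the floor after withdrawal. It is relevant to ERT-treated Part 1 participants with low expression, most plausibly in leukocytes, DBS or the low doses.
- **Zero parameters.** A rule is missing. The event is unlikely with strong expression but possible for a low or non-expresser, and with about 12 participants in Part 1 the loss of one or two would matter.

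The documents do not establish that the endpoint will be biased, or that a dosing decision rests on the fitted slope.

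**What to change.** 1. State in SAP 10.1 that the floor does not apply to the 10.2 change-from-baseline tables, report signed changes there, and say which baseline they use.
2. Reconcile the PK baseline with the pre-dose trough wording in Protocol 8.1. Flag each GCase sample as on or off ERT/SRT, with time since the last ERT infusion where recorded. Add a sensitivity summary that separates on-ERT from off-ERT data, alongside the planned baseline-to-Week-38 AUC. It should not replace that AUC: withdrawal depends on achieved GCase, so restricting to post-withdrawal samples would select on response.
3. Keep the log-log power model. Pre-specify how a Cmax or AUClast of zero is handled: report the number affected by cohort, give a sensitivity fit that retains them (for example as left-censored), show the n behind each geometric mean, and report the slope with a confidence interval. Fitting the power function directly on the raw scale is not a good substitute. In a simulation with true slope 1, between-person log SD 0.5 and three per dose, the SD of its slope was 0.30, against 0.12 for log-log.

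The cost is SAP wording and some programming. Gaucher therapy is already recorded (Protocol 11.1). If the floor would otherwise have been used in 10.2, mean changes may look slightly less favourable.
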